### 10.4.4 Handling of missing values/censoring/discontinuations

A patient who has not progressed or died at the date of the analysis cut-off would have his/her PFS and OS censored at the time of the last adequate assessment before the cut-off date. Any disease assessment indicating response status other than “unknown” or “not done” is considered an adequate response assessment.

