### 10.5.2 Other secondary efficacy objectives

The secondary objectives of the study:

- To assess progression free survival (PFS) based on local investigator assessment per RECIST 1.1 or other appropriate hematological response criteria
- To assess overall survival
- To assess duration of response (DOR) based on local investigator assessment per RECIST 1.1 or other appropriate hematological response criteria
- To assess safety and tolerability

The secondary efficacy variable progression free survival (PFS) is defined as the time from the date of first dose to the date of first documented disease progression or relapse or death due to any cause.

PFS will be summarized and graphed using the Kaplan-Meier product-limit method for each patient group. Patients who drop-out without progression will be censored at the time of last adequate assessment. The estimates of the 25th, median, 75th percentiles of the PFS and their 95% confidence intervals will be provided, if applicable.

Overall survival (OS) is defined as the time from the date of first dose to the date of death due to any cause. If a patient is not known to have died, survival time will be censored at the date of the last contact.

OS will be summarized and graphed using the product-limit method as above.

The duration of response applies only to patients whose best response was PR or CR. For patients with solid tumors the assessment criteria will be RECIST 1.1 and will include responses of CR and/or PR. For hematologic tumors other appropriate hematological response criteria will apply and are included in the appendices. The duration of response is defined as the time from the first documented response to the date first documented disease progression or relapse or death due to any cause. The duration of response will be summarized descriptively for each patient group.

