### 3.2.3 New lesions

The appearance of a new lesion is always associated with Progressive Disease (PD) and has to be recorded appropriately in the eCRF.

- If a new lesion is **equivocal**, for example because of its small size, continued therapy and follow-up evaluation will clarify if it represents truly new disease. If repeat scans confirm there is definitely a new lesion, then progression should be declared using the date of the first observation of the lesion

- If new disease is observed in a region which **was not scanned at baseline** or where the particular baseline scan is not available for some reason, then this should be considered as a PD. The one exception to this is when there are no baseline scans at all available for a patient in which case the response should be UNK, as for any of this patient's assessment.
- A **lymph node is considered as a “new lesion”** and, therefore, indicative of progressive disease if the short axis increases in size to  $\geq 10$  mm for the first time in the study plus 5 mm absolute increase.
  - a. Negative FDG-PET at baseline, with a positive FDG-PET at follow-up is a sign of PD based on a new lesion.
  - b. No FDG-PET at baseline and a positive FDG-PET at follow-up: If the positive FDG-PET at follow-up corresponds to a new site of disease confirmed by CT, this is PD. If the positive FDG-PET at follow-up is not confirmed as a new site of disease on CT, additional follow-up CT scans are needed to determine if there is truly progression occurring at that site (if so, the date of PD will be the date of the initial abnormal FDG-PET scan). If the positive FDG-PET at follow-up corresponds to a pre-existing site of disease on CT that is not progressing on the basis of the anatomic images, this is not PD

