In addition, with all solid tumor types combined and separately for each hematological tumor type, the clinical benefit rate (CBR) will be provided with its 95% exact confidence interval (CI) (using clopper-pearsone¹ method); overall response rate (ORR, e.g., partial response [PR] and complete response [CR] for solid tumor) and its 95% CI will be presented. Summary on numbers and percentages of patients for each response category (e.g., for solid tumor - CR, PR, stable disease [SD], progressive disease [PD], not evaluable [NE]) will also be provided. For tumor types that have ten (10) or more patients, separate summaries will be performed by the tumor type using the same methodology. In the event that there are fewer than 4 patients for a hematological tumor type, only listing will be provided.

Duration of response (DOR) based on local investigator assessment will also be analyzed. Progression-free survival (PFS) and overall survival (OS) will be summarized using Kaplan-Meier (KM) methodology.

Patient demographics, disease characteristics (including mutation analyses), ribociclib treatment, and safety variables will be analyzed descriptively.

Details of the above analyses are presented in the following sections.

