4.3 Duration of response

DOR applies only to patients who responded, e.g., for solid tumor, responder is defined as the patient's best overall response being CR or PR. The start date is the date of first documented response, and the end date is the date of event defined as the first documented progression/relapse or death due to any cause within 30 days of the last study drug dose date. In other words, the start date will be determined using the time the response was first determined and not using the time the response was confirmed. If a patient has not had an event, duration is censored at the date of last adequate tumor assessment. Distribution of DOR will be estimated using the Kaplan-Meier method and the median response duration will be

presented along with 95% confidence interval only if there are sufficient numbers of events, otherwise, only listing of DOR will be provided. Analyses will be based all tumor types combined.

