4.4 Progression Free Survival (PFS)

PFS is defined as the time from the date of first dose of ribociclib to the date of the first documented disease progression/relapse or death due to any cause within 30 days of the last study drug dose date, and is calculated as $PFS = (\text{date of progression/relapse or death} - \text{date of first study treatment} + 1)$. Disease progression noted as the reason for discontinuation of treatment will also be considered as a progression event for PFS analyses.

Patients who discontinue or complete study treatment without disease progression will be censored at last adequate tumor assessment on or before the discontinuation/completion of the study. For patients who are still on study treatment at the time of data cut-off date for the primary analyses, PFS will be censored at the last adequate tumor assessment before the data cut-off date for the analysis of PFS for the primary CSR. Patients who do not have any post baseline tumor assessment will be considered as censored at Day 1.

PFS will be summarized and graphed using the Kaplan-Meier product-limit method². The estimated median survival time, the corresponding 95% CIs³, and 25th and 75th percentiles will be provided. In addition, survival-rate estimates with 95% CIs will also be provided at time points, such as 1, 2, 3, 4, 5, 6, 9 and 12 months. Analyses will be based on all tumor types combined. For tumor types that have ten (10) or more patients, separate summaries will be performed by the tumor type.

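### The definition of an adequate assessment does not exclude RECIST 'not evaluable' (NE), so PFS in solid tumours can be censored at a scan that did not assess all target lesions (minor; descriptive secondary endpoints only)

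*Protocol*

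**What the plan says.** Protocol 10.4.4 says that a patient without progression or death "would have his/her PFS and OS censored at the time of the last adequate assessment before the cut-off date". It then defines the term: "Any disease assessment indicating response status other than “unknown” or “not done” is considered an adequate response assessment". No other section of either document defines 'adequate'. (The OS half of the first sentence conflicts with Protocol 10.5.2 and SAP 4.5, which use last contact. That is a separate matter.)

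The term is then used in three places:

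- Protocol 10.5.2, PFS: "Patients who drop-out without progression will be censored at the time of last adequate assessment".
- SAP 4.4, PFS: "Patients who discontinue or complete study treatment without disease progression will be censored at last adequate tumor assessment". Patients with no post-baseline tumour assessment at all are censored at Day 1.
- SAP 4.3, DOR: "If a patient has not had an event, duration is censored at the date of last adequate tumor assessment".

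On status labels for solid tumours, Appendix B Table 3-1 assigns NE when target lesions are not all evaluated, non-target disease is not progressing and there is no new lesion. Tables 3-2 and 3-3 also carry NE. SAP 2.2 and 4.2 list CR, PR, SD, PD and NE as the solid-tumour categories, with no 'unknown' category. Appendix B 3.2.3 reserves UNK for another situation: "no baseline scans at all available for a patient in which case the response should be UNK".

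**The concern.** NE is a status other than 'unknown' or 'not done'. A programmer who applies 10.4.4 as written will keep an NE scan as an adequate one. Censoring then falls on a date at which target-lesion progression had not been excluded, and the patient stays in the PFS risk set up to that date.

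Two things are at stake. First, the error runs in one direction. Counting NE scans leaves the events unchanged and moves some censoring times later. Later censoring can only enlarge the risk sets, so each Kaplan-Meier step is the same size or smaller and the curve cannot fall.

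Second, the handling differs by tumour type for no stated reason, although SAP 4.4 pools all tumour types in one PFS curve.

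**Working it through.** The plan states no figure that depends on this definition, so there is none to reproduce. The check has two parts.

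**1. The same gap under each set of response criteria**

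| Criteria | Situation | Label | Adequate under 10.4.4, read literally? |
|---|---|---|---|
| RECIST, Appendix B Table 3-1 | target lesions not all evaluated | NE | yes |
| RECIST, Appendix B 3.2.3 | no baseline scans | UNK | no |
| Lymphoma, Appendix C 4.1.3 | an index-lesion measurement missing, no progression seen | Unknown (UNK) | no |
| AML, Appendix F | assessment incomplete | Unknown | no |

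The Day 1 rule in SAP 4.4 does not close the gap. It covers patients with no post-baseline assessment, and a patient whose only scan is NE has had one.

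**2. Size**

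*One patient.* Scheduled assessments fall at weeks 8 and 16 and every 16 weeks after that (Protocol 4.1.1). Take SD at week 8, NE at week 16, then a stop for a reason other than progression. Censoring is at week 16 if NE is adequate and at week 8 if not, a difference of 8 weeks. For SD at week 16 and NE at week 32 the difference is 16 weeks. End-of-treatment or unscheduled scans would change these intervals.

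*The PFS curve, limited NE.* Assumptions, none of them from the documents: exponential PFS with median 8 to 16 weeks, 10-20% of patients leaving without progression, and 5-30% of those having NE as their last scan. The share of all patients affected is 0.10 × 0.05 = 0.5% up to 0.20 × 0.30 = 6%. Simulated Kaplan-Meier curves under the two rules (60,000 patients per setting, scans at weeks 8, 16, 32, 48 and 64) differ by 0.04 to 0.7 percentage points at 4 and 6 months. With about 12-29% leaving (0.12 × 0.05 = 0.6% to 0.29 × 0.30 = 8.7% affected), the difference is about 0.1 to 1.7 points.

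*The PFS curve, frequent NE.* Assume instead that at every visit a fraction q of the patients still on study have an NE scan that is also their last, unrelated to progression. Let m be the median in weeks, so that p = 1 − 2^(−8/m) is the chance of progression in each 8-week interval. Then, at week 16:

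- NE excluded: S = (1 − p)².
- NE adequate: S = (1 − (1 − q)p)².

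| m (weeks) | p | q | NE excluded | NE adequate | Difference (points) |
|---|---|---|---|---|---|
| 8 | 0.500 | 0.05 | 0.250 | 0.276 | 2.6 |
| 8 | 0.500 | 0.20 | 0.250 | 0.360 | 11.0 |
| 12 | 0.370 | 0.10 | 0.397 | 0.445 | 4.8 |
| 16 | 0.293 | 0.05 | 0.500 | 0.521 | 2.1 |
| 16 | 0.293 | 0.20 | 0.500 | 0.586 | 8.6 |

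Simulation agrees (for m = 12 and q = 0.10: 0.396 and 0.445).

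If NE is twice as likely once the patient has progressed, 16-week PFS is overstated by about 4 to 24 points with NE adequate. With NE excluded it is still overstated by about 1.4 to 8.6 points, so the fix reduces that bias without removing it.

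**The case against.** The best defence is that 'unknown' was meant to include NE. Appendices F, H and I (AML, ALL, CML) define Unknown to cover an assessment not done, a missing baseline and an incomplete assessment together, and lymphoma does much the same. The SAP's solid-tumour list has NE and no 'unknown', which suggests one non-assessable class under two names. This is a plausible account of intent. But those appendices are disease-specific, nothing applies them to RECIST, and Appendix B prints both labels for different situations. The text still needs the clarification.

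Other objections do stand and limit the point:

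- A reader might infer that, with few responders (3 partial responses among 114 evaluable patients in the phase I study, Protocol 1.2.1.2.2), a single NE scan could move the median DOR. The SAP does not support this. Section 2.3 lists DOR only when the response rate is low, and section 4.3 gives a median only when there are enough events. Nor does 10.4.4 name DOR, which is reached only through SAP 4.3.
- A reader might also infer that the added time was not observed at all. Under Table 3-1, NE requires non-target disease that is not progressing and no new lesion. Only target-lesion growth is left open.
- The larger figures above should not be read as expected bias. They make every NE scan the patient's last. The setting that links NE to progression also leaves those progressions unrecorded, whereas SAP 4.4 counts progression given as the reason for stopping treatment, and deaths within 30 days of the last dose, as events.
- Table 7-1, footnote 3, requires an end-of-treatment scan when the last scan showed no progression and was at least 8 weeks earlier. That narrows the affected group to patients who stop within about 8 weeks of an NE scan, or whose end-of-treatment scan is also NE.

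**Conclusion.** The point holds as a minor one. As written, 10.4.4 makes an NE scan adequate in RECIST-assessed tumours, while the equivalent scan in lymphoma or AML is not. The result is a censoring rule that depends on a label and can only lengthen PFS.

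The size cannot be fixed from the documents, because they give no NE rate. It is below about 1 percentage point on the PFS curve with 10-20% of patients leaving without progression and 5-30% of those ending on an NE scan. It is larger only if final NE scans are common. No effect on a DOR median should be claimed.

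SAP 2.2 makes every analysis other than the primary one descriptive. The primary clinical benefit rate does not use this censoring rule, so no success or futility decision is affected.

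**What to change.** State in Protocol 10.4.4, and by reference in SAP 4.3 and 4.4, that:

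- an assessment with overall response NE, unknown or not done is not adequate;
- every other response category defined in the protocol is adequate, including non-CR/non-PD and the haematological categories such as 'no response', so that one unclear label is not replaced by another;
- the Day 1 rule in SAP 4.4 applies to any patient with no adequate post-baseline assessment, not only to those with no assessment.

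The cost is a short text change and one filter in the censoring program. Some censoring times become shorter.

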### 10.4.5 Supportive analyses

Not applicable.

## 10.5 Secondary objectives

### 10.5.1 Key secondary objective(s)

The key secondary objective of this study is to assess Overall Response (OR) of Partial Response (PR) or Complete Response (CR) based on local investigator assessment.

For patients with solid tumors the assessment criteria will be RECIST 1.1 and will include responses of CR and/or PR. For hematologic tumors other appropriate hematological response criteria will apply and are included in the appendices.

The overall response rate (ORR, PR plus CR) and its 95% exact confidence interval will be provided for each patient group. In the event where sample size in each patient group is small (<10), only ORR summary for entire study cohort will be presented.

### 10.5.2 Other secondary efficacy objectives

The secondary objectives of the study:

- To assess progression free survival (PFS) based on local investigator assessment per RECIST 1.1 or other appropriate hematological response criteria
- To assess overall survival
- To assess duration of response (DOR) based on local investigator assessment per RECIST 1.1 or other appropriate hematological response criteria
- To assess safety and tolerability

The secondary efficacy variable progression free survival (PFS) is defined as the time from the date of first dose to the date of first documented disease progression or relapse or death due to any cause.

PFS will be summarized and graphed using the Kaplan-Meier product-limit method for each patient group. Patients who drop-out without progression will be censored at the time of last adequate assessment. The estimates of the 25th, median, 75th percentiles of the PFS and their 95% confidence intervals will be provided, if applicable.

Overall survival (OS) is defined as the time from the date of first dose to the date of death due to any cause. If a patient is not known to have died, survival time will be censored at the date of the last contact.

OS will be summarized and graphed using the product-limit method as above.

The duration of response applies only to patients whose best response was PR or CR. For patients with solid tumors the assessment criteria will be RECIST 1.1 and will include responses of CR and/or PR. For hematologic tumors other appropriate hematological response criteria will apply and are included in the appendices. The duration of response is defined as the time from the first documented response to the date first documented disease progression or relapse or death due to any cause. The duration of response will be summarized descriptively for each patient group.

### **10.5.3 Safety objectives**

For all safety analyses, the safety set will be used. All listings and tables will be presented by patient groups.

The assessment of safety will be based mainly on the frequency of adverse events and on the number of laboratory values that fall outside of pre-determined ranges. Other safety data (e.g., electrocardiogram, vital signs) will be considered as appropriate. All safety data will be listed.

The safety summary tables will include only assessments collected no later than 30 days after study treatment discontinuation. Those collected later than 30 days after study treatment discontinuation will be flagged in listings.

#### **10.5.3.1 Analysis set and grouping for the analyses**

##### **10.5.3.1.1 Adverse events (AEs)**

All adverse events recorded during the study will be summarized. The incidence of treatment-emergent adverse events (new or worsening from baseline) will be summarized by system organ class and/or preferred term, maximum severity (based on CTCAE v4.03), type of adverse event, relationship to the study treatment by treatment group. Deaths reportable as SAEs and non-fatal serious adverse events will be listed by patient and tabulated by type of adverse event and patient group.

Adverse events will be summarized by presenting the number and percentage of patients by system organ class and/or preferred term, the maximum severity (based on CTCAE v4.03) and treatment arm. Adverse events related to study treatment will also be summarized. In

addition, adverse events of related nature may be analyzed by categories regrouping the relevant preferred terms, as appropriate.

#### 10.5.3.1.2 Laboratory abnormalities

All laboratory values will be converted into SI units and the severity grade will be calculated using appropriate common terminology criteria (CTCAE v4.03).

A severity grade of 0 will be assigned when the value is within normal limits. For lab parameters for which severity grades are determined both through normal limits and absolute cut-offs, in the unlikely case when a local laboratory normal range overlaps into the higher (i.e. non-zero) CTCAE grade, the laboratory value will still be taken as within normal limits and assigned a CTCAE grade of zero.

A listing of laboratory values will be provided by laboratory parameter, patient, and treatment arm. A separate listing will display notable laboratory abnormalities (i.e., newly occurring CTCAE grade 3 or 4 laboratory toxicities). Lab values collected later than 30 days after study treatment discontinuation will be flagged in the listings

The following by-group summaries will be generated separately for hematology, and biochemistry parameters:

[figure not shown]
- shift tables using CTCAE grades to compare baseline to the worst on-treatment value
- for laboratory tests where CTCAE grades are not defined, shift tables using the low/normal/high/(low and high) classification to compare baseline to the worst on-treatment value.
- listing of all laboratory data with values flagged to show the corresponding CTCAE grades and the classifications relative to the laboratory normal ranges.

[figure not shown]
#### 10.5.3.1.3 Other safety data

Summary statistics for data from other tests will be provided, notable values will be flagged, and any other information collected will be listed as appropriate.

Descriptive summary statistics will be provided for :

- Electrocardiograms: changes from baseline to last available ECG results
- Cardiac imaging: number and percentage of patients with notable LVEF values
- Vital signs: number and percentage of patients with at least one post-baseline vital sign abnormality
- ECOG performance status: shift table comparing baseline to worst post baseline ECOG performance status.
- All other safety related procedures as required
- Listings with flagged notable values and any other information collected will be provided as appropriate.

## 10.7 Interim analysis

Scheduled interim data reviews will occur for the primary endpoint of clinical benefit rate only as required by the Bayesian Hierarchical design. The first interim data review will be performed after the first 30 patients overall (across all groups) have been dosed for at least 16 weeks or discontinued, and then every 13 weeks thereafter, then every 13 weeks thereafter. Interim analyses may be performed more frequently dependent on enrollment rate to avoid over-enrollment in any of the disease cohorts. At each interim analysis, the groups will be evaluated for early futility and early success by comparing posterior quantities for the response rate to pre-specified early stopping criteria.

There is no plan for a formal interim analysis of safety or other secondary endpoints for this study. However, for publication or other purposes, interim data review of clean data will be performed as necessary. At these interim reviews, patient demographics/baseline characteristics, the primary and secondary endpoints as applicable, and all important safety endpoints will be summarized. No formal report will be issued for these data reviews.

